5.0 Study Procedures

This study will be performed using a crossover design. Each subject will act as her own control. Subjects will be randomized to the order that they receive either the study medication or the placebo. A random number generator will be used to determine the order of randomization. Subjects will be randomized during their first visit to the Indiana Clinical Research Center (ICRC) after informed consent has been obtained.

This study will be conducted at the ICRC. All subjects will undergo a screening visit (visit 1) that will include obtaining of a 12-lead ECG, performance of a history and physical examination, obtaining height and weight, and bloodwork. Using a two-way crossover design, each subject will be studied **two times**, serving as her own control. During each phase, subjects will receive a single IV dose of ibutilide 0.003 mg/kg, which will be administered by an ICRC nurse.^{9,10} Each subject will **take oral progesterone 400 mg orally once daily in the evening**, or use **matching placebo** daily in the evening for 7 days. The crossover order will be randomized. The study design is summarized below in Figure 1:

[figure not shown]

Figure 1. Study design

This study will be conducted with 3 visits: visit one is a screening visit; visits 2 and 3 includes 7 days of medication self-administration followed by a 10 hour ICRC visit. There will be a minimum 14-day washout period between visits 2 and 3. In premenopausal women, during each phase, subjects will be studied during the ovulation phase of the menstrual cycle. The ovulation phase is selected for this study rather than the luteal phase because, while serum estradiol is similar in the two phases, the natural progesterone:estradiol ratio is lower in the ovulation phase.⁹ In order to time the administration of ibutilide and measurement of on-drug QT intervals to the ovulation phase, premenopausal women with a typical 28-day menstrual cycle will begin taking their study medication on the 5th day of their menstrual period (see Figure 2). For women who typically have longer menstrual cycles (30-35 days), study drug therapy will be initiated on the 6th or 7th day of their menstrual periods (Figure 2).

[figure not shown]

Figure 2. Hormone fluctuation during the menstrual cycle.

Visit 1 (Screening visit):

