Continuous ECG monitoring will be initiated 30 minutes prior to ibutilide and will continue until the post-ibutilide Bazett's-corrected QT interval is < 450 ms, which generally occurs within 2 hours following administration of this low, subtherapeutic dose of ibutilide. Three 12 lead ECGs approximately one minute apart (three ECGs within a total of 5 minutes) will be selected for QT interval measurement before (time 0) and after ibutilide at: at 5 minutes during infusion, end of infusion, 5, 10, 15, 20, 30 and 45 minutes and 1, 2, 4, 6, and 8 hours. Blood (6 mL) for determination of ibutilide concentrations will be obtained from the indwelling catheter in the arm contralateral to that into which ibutilide infused was approximately the following times (within 5 minutes of the times listed) 5 minutes during infusion, at the end of infusion, and 5, 10, 15, 20, 30 & 45 minutes, and 1, 2, 4, 6, and 8 hours following end of infusion. An 8-hour data collection and monitoring period is sufficient, as QT_c intervals return to baseline within 2-6 hours.^{9,10}

In addition, blood will be drawn to determine serum progesterone, estradiol, and potassium concentrations at the same time as the time 0 ibutilide concentration is drawn. If the subjects is found to have hypokalemia as defined in the exclusion criteria, then they will be withdrawn from the study.

At 3-7 days following the study visit, subjects will be called/texted or emailed based on preference to assess for any potential adverse events related to study medications or procedures.

Following visit 3, subjects' participation in the study will be complete.

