In all of the published literature, the overall incidence of TdP associated with ibutilide is 2.0%. TdP has never been reported at the dose that we propose to administer in this study. The lowest dose of ibutilide that has ever been associated with TdP in the published literature is 0.5 mg, and there has only been one reported case at this dose. That is more than double the dose that we propose to administer. In order to achieve this dose in our study, a patient would have to weight 166 kg (based on our dose of 0.003 mg/kg). No subject in this study will receive a dose as high as 0.5 mg, because we have an upper weight exclusion of 135 kg. Therefore, this risk of TdP in our volunteer subjects, at a low dose of 0.003 mg/kg (roughly 20% of the lowest clinical dose), is extremely low, and again, TdP has never been reported at this low dose.

Oral progesterone 400 mg once daily is the dose that was effective for attenuating drug-associated QTcI interval response in premenopausal women. Oral progesterone 400 mg daily has been administered to pre-menopausal women with minimal adverse events including abdominal cramping, nausea, vomiting, mood disturbances and menstrual spotting or bleeding following withdrawal of the medication. Subjects will be monitored via phone calls throughout the dosing period and advised to discontinue the medication if adverse events become intolerable.

Risks related to the blood draws and intravenous catheter placement will be minimized through the use of experienced staff placing the intravenous catheter. Subjects will be evaluated for anemia prior to inclusion in order to minimize the risk of anemia due to blood draws.

Safety Monitoring

Any serious or unexpected adverse event will be reported to the Research and Sponsored Programs Committee on the IUPUI campus within 3 working days of notification of the event. A written report of the adverse event will also be submitted. Any Serious Adverse Event (SAE) that is observed during the study or within 30 days after administration of ibutilide will be recorded and reported to the SAE contact investigator. The SAE contact investigator will serve as the chair for the Data and Safety Monitoring Board (DSMB).

A Data Safety & Monitoring Board (DSMB) has been established for this study. The DSMB will be chaired by [name], PhD, Assistant Professor of Obstetrics & Gynecology, School of Medicine, Indiana University. The other members of the DSMB are:

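### The 30-day SAE window outlasts the last scheduled contact, so 23 to 27 of the 30 days after the final ibutilide dose rest on spontaneous reports

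*Combined protocol and SAP*

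**What the plan says.** Section 6.0, Safety Monitoring, sets the window: any SAE seen while the study runs or "within 30 days after administration of ibutilide will be recorded and reported to the SAE contact investigator". A separate sentence in the same place gives three working days for reporting serious or unexpected events, counted from when the event is notified.

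Section 5.0 sets the contacts. The study has three visits; ibutilide is given at Visits 2 and 3, and no visit follows Visit 3. After each of those two visits the same instruction appears: "At 3-7 days following the study visit, subjects will be called/texted or emailed based on preference to assess for any potential adverse events". The Visit 3 text then closes with: "Following visit 3, subjects' participation in the study will be complete".

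Section 5.0 also places at least 14 days of washout and then 7 days of study medication between the two ibutilide visits, with Visit 3 on the day after the seventh dosing day. Section 7.0 covers withdrawal but describes no safety contact after it.

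**The concern.** The plan sets a window of 30 days, but its schedule asks subjects about events only up to day 7 at the latest after the last dose. The reporting clock does not help, because it starts only when someone learns of the event. An SAE here includes a hospitalisation or a death from any cause. Late in the window such an event reaches the team only if the subject, or someone acting for her, gets in touch after she has been told that her participation is over.

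What is at stake is how a count of late SAEs can be read. After the first dose, a count of zero would come largely from asking. After the second, it would come mostly from not having been told. The two zeros carry different information, and nothing in the plan warns the reader of this.

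**Working it through.** The 30 days are a design choice, so there is no planned figure to reproduce. The check is calendar arithmetic.

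**Inputs**
- Window: 30 days after an ibutilide dose (Section 6.0, Safety Monitoring).
- Contact after each ibutilide visit: day 3 to day 7 (Section 5.0, Visits 2 and 3).
- Contacts after that one following Visit 3: none found in the documents.
- Interval between the two doses: at least 14 days of washout, 7 days of dosing, and Visit 3 the next day (Section 5.0).
- Planned subjects: 40, with 20 in each treatment order (Sections 4.0 and 5.0).

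**Formula**

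Days without active enquiry = 30 − day of the last scheduled contact, with a minimum of 0.

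**Second dose (Visit 3)**
- Contact on day 7: 30 − 7 = 23 days; 23/30 = 77%.
- Contact on day 3: 30 − 3 = 27 days; 27/30 = 90%.

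**First dose (Visit 2), subjects who complete**

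The earliest Visit 3 is 14 + 7 + 1 = 22 days after Visit 2, or day 21 if the visit day is counted as the first washout day. The contact after Visit 3 then falls as follows.

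| Visit 3 at | Contact at | Days left in the first window |
|---|---|---|
| day 21 | day 24 to 28 | 6 to 2 |
| day 22 | day 25 to 29 | 5 to 1 |
| day 28 (one 28-day cycle) | day 31 to 35 | 0 |

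The first window is therefore covered except for 1 to 6 days at the shortest washout. It is fully covered when the doses are a 28-day cycle apart.

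**First dose, subjects who withdraw after the contact following Visit 2**

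If there is no further contact, the result is the same as after Visit 3: 23 to 27 of 30 days.

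**Split by treatment**

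Group A takes progesterone second and Group B takes placebo second, 20 subjects each. If all complete, the days without enquiry after Visit 3 number 20 × 23 = 460 to 20 × 27 = 540 in each group, so the same amount falls after progesterone as after placebo.

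**With a day-30 contact after the last dose**

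30 − 30 = 0 days, for completers and for those who withdraw after Visit 2.

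**The case against.** **The two sections do not strictly conflict.** Section 6.0 speaks of SAEs that are observed, and the reporting clock runs from notification. Both can be read as a duty to record what comes to attention, not a promise to ask until day 30. This stands. A late SAE that a subject volunteers would still be recorded, so the gap is in active ascertainment.

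**The consequence is small.** By the protocol's account, ibutilide is given once per phase at a subtherapeutic dose, has no active metabolites, and lets QTc return to baseline within 2 to 6 hours. Subjects are observed for 8 hours and are not discharged with a QTc above 450 ms. Acute ibutilide events should therefore appear at the visit or by the 3-to-7-day contact. Randomised order also spreads the late gap over both treatments. These points stand and limit the weight of the concern.

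**The consent form may ask subjects to report later events.** Those pages are not available, so this cannot be excluded. Such an instruction would still be passive collection.

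**Two stronger readings are tempting, and the documents support neither.**
- A reader might infer that the DSMB or the final report would present complete 30-day SAE data. No section plans a 30-day SAE table or claims completeness, and SAEs are not among the endpoints or analyses in Section 8.0.
- A reader might infer that events in the 7-day dosing periods also go unasked, because Section 5.0 lists no calls there. But Section 6.0 says: "Subjects will be monitored via phone calls throughout the dosing period". It belongs to the same protocol. Subjects also keep a diary of adverse effects in both periods, and the ibutilide visit follows the day after dosing ends. Those calls should stay in the plan.

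**Conclusion.** The concern holds as a gap in active SAE follow-up after the last ibutilide dose. Of the 30 days that the plan itself chose, 23 to 27 (77% to 90%) after Visit 3 are covered only by spontaneous reports. The same is true after Visit 2 for a subject who withdraws before any further contact. In completers the first dose leaves at most about 1 to 6 days uncovered.

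The likely impact is modest, and no bias between progesterone and placebo is expected. The endpoints and their analysis are not affected. What suffers is the completeness of late safety data in the second period compared with the first.

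This rests on three assumptions: the 3-to-7-day contact is made as scheduled; no later contact is arranged in material outside the documents; and the two treatment orders are close to equal in size, with similar withdrawal. A change is worth making because it is cheap, not because a serious safety failure has been shown.

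**What to change.** - In Section 5.0, add one call, text or email at about day 30 after each subject's last ibutilide dose, by the method already used at 3 to 7 days, to ask about SAEs since the previous contact.
- In Section 7.0, apply the same contact to subjects who withdraw after Visit 2, as far as they agree to be contacted.
- Move the end of participation from Visit 3 to that contact. This also removes a small oddity: read literally, participation now ends before the 3-to-7-day contact has taken place.
- The DSMB meets after 10, 20 and 30 subjects have completed the study. State whether completion for this purpose means Visit 3 or the day-30 contact, so that the change does not delay those meetings unintentionally.

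**Cost:** one short contact per subject dosed with ibutilide, so at most about 40 for the planned 40 subjects, plus the protocol wording. No visit, sample or ECG is added. Each subject's participation is formally about 30 days longer after Visit 3, and the study-duration statement in Section 5.0 should say so.

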7.0 Study Withdrawal/Discontinuation

Subjects may withdraw from the study at anytime during the study. If a subject wishes to withdraw from the study, he/she may call the principal investigator and withdraw himself/herself from the study. The subject will receive compensation for their time up to the period of withdrawal.

The principal investigator may withdraw a subject from the study for the following reasons: a change in the subject' medical condition resulting in an increased risk profile, change in any inclusion or exclusion criteria for the subject, or subject unwilling or unable to complete part of the protocol as stated. If the PI determines that a subject needs to be withdrawn from the study, he will contact the subject by phone and also in writing. The subject will receive compensation for any part of the study that he/she has completed.

8.0 Statistical Considerations

Statistical analysis will be performed separately for the two subject populations:

- Postmenopausal women (progesterone vs placebo)
- Premenopausal women (progesterone vs placebo)

QT intervals will be corrected for heart rate using two correction methods, the Fridericia (QT_F) and Framingham (QT_{Fra}) methods.

Study Endpoints: Comparison of progesterone and placebo phases for: 1) Baseline (pre-ibutilide) maximum QT_F & QT_{Fra} 2) Ibutilide effect on maximum QT_F & QT_{Fra}, 3) Ibutilide effect on maximum % change in QT_F & QT_{Fra}, and 4) Ibutilide effect on AUEC_{0-1.17} and AUEC_{0-8.17}. Endpoints will be correlated with progesterone concentrations. 5)

Statistical analyses: Means (standard deviations) or medians (interquartile range) will be presented for continuous variables. Distribution normality will be assessed using the Kolmogorov-Smirnov test. Paired t-test (if normality holds) or signed-rank test (if normality does not hold) will be used to compare outcome measures between the two treatment phases; 95% confidence intervals will be calculated. SAS 9.4 (Cary, NC) will be

used. Correlations between the primary endpoints and serum progesterone concentrations will be performed using Pearson's correlation coefficient.

Anticipated Outcomes: During the progesterone phase, the following outcome measures will be significantly lower than vs placebo: 1) Pre-ibutilide QT_F and QT_{Fra}; 2) Post-ibutilide maximum QT_F and QT_{Fra}; 3) AUEC 1 hour and 8 hours after ibutilide; 4) Post-ibutilide % change in maximum QT_F and QT_{Fra}, 5) J-T_{peak} and T_{peak-T_{end}}.

Sample Size Calculation: In this 2-way crossover study, at a two-sided α level of 0.05 and a power of 0.80, a sample size of 20 subjects in the postmenopausal population and n=20 subjects in the premenopausal population will be sufficient to detect a difference in maximum QT_F and QT_{Fra} of 15 ms, assuming a QT_F and QT_{Fra} interval prolongation of 24±12 ms associated with ibutilide in the absence of progesterone.

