4.0 Enrollment/Randomization

Subject Recruitment:

Forty volunteer subjects (n=20 postmenopausal women, n=20 premenopausal women) will be recruited through 2 methods:

- Potential subjects will be recruited through the use of a recruitment database maintained through the CTSI InResearch Volunteer research database. Potential volunteers who meet inclusion criteria will be contacted via email and will be offered the opportunity to participate in this study.
- Advertisements will be placed in public locations throughout the IUPUI campus. Purdue University Research volunteers website, publications targeted at seniors and on the IU Health website asking for volunteers. Potential subjects will call or Email the PI or research coordinator if interested in participating in the study.

During the initial phone call with the potential subject, the investigator will explain the purpose of the study, study procedures and risks associated with the study. If the potential subject is interested in participating, the investigator will then ask the potential subject specifically about inclusion and exclusion criteria. If the subject meets all inclusion criteria and had no exclusion criteria, the screening visit will be scheduled. A letter will be Emailed or sent via US mail to the subject containing the following information:

- Location of the Clinical Research Center
- Brief explanation of the CRC setting and study activities that will take place there
- What subjects should bring with them (their current medications)
- Directions to IU Health University Hospital and to the CRC and where to park
- That they will be given lunch and that their parking will be reimbursed

- A copy of the informed consent form for them to review

Prior to Visit 1, the screening visit, an investigator will telephone, Email or text the subject (whichever the subject prefers) to remind them of their visit, review the consent form, and answer any questions they may have. This does not constitute the official review of the consent form with the subject but provides an opportunity to answer questions that the subject may have prior to them appearing for the screening visit.

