Subjects will be asked to come to the ICRC at IU Health University Hospital. An investigator will review the procedures and risks of the study in detail and obtain written informed consent. After written informed consent is obtained, subjects will undergo a screening history and physical examination performed by an investigator. Three 12-lead ECGs one minute apart (QTc will be averaged across ECGs to determine eligibility), height, weight and blood work will be obtained at this time to determine serum potassium, magnesium, liver enzymes, hematocrit. Premenopausal women will undergo a urine human chorionic gonadotropin (HCG) test to rule out pregnancy.

Once laboratory results are obtained and the physical is completed and the subject has met inclusion criteria and has no exclusion criteria, the subject will be enrolled in the study. If the subject meets any exclusion criteria, they will not be allowed to proceed in the study. This process will take approximately 1 hour.

Immediately following the screening history and physical examination, subjects will be randomly assigned to two groups:

Group A: (n= 20 subjects)

Each subject will take two placebo capsules once daily in the evening for 7 days.

Group B: (n= 20 subjects)

Each subject will take oral progesterone 400 mg orally once daily (two x 200 mg capsules) in the evening for 7 days.

Subjects will be sent home with one week's supply of the study medication to which they are initially randomized and a medication diary with which to keep track of when they take the medication, any adverse effects they may experience, and any changes in their own

concurrent medications. They will receive written and verbal instructions about the study medication and dates will be established for Visit 2.

Visit 2:

Prior to the visit subjects will be NPO and remain NPO until 4 hours after the end of the ibutilide dosing. Subjects may drink non-caloric drinks during this period such as coffee, tea, diet soda, water ect. If the serum potassium concentration is low as defined previously in the protocol, then the subject may have orange juice or a banana as previously defined in the protocol.^{26,27,28}

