Continuous ECG monitoring will be initiated prior to ibutilide administration and will continue until the post-ibutilide Bazett's-corrected QT interval is < 450 ms, which generally occurs within 2 hours following administration of this low, subtherapeutic dose of ibutilide. Three 12 lead ECGs approximately one minute apart (three ECGs within a total of 5 minutes) will be selected for QT interval measurement before ibutilide administration and after ibutilide at: at 5 minutes during infusion, end of infusion, 5, 10, 15, 20, 30 and 45 minutes and 1, 2, 4, 6, and 8 hours. Blood (6 mL) for determination of ibutilide concentrations will be obtained from the indwelling catheter in the arm contralateral to that into which ibutilide was infused at approximately the following times (within 5 minutes of the times listed) 5 minutes during infusion, the end of infusion, and 5, 10, 15, 20, 30 & 45 minutes, and 1, 2, 4, 6, and 8 hours following end of infusion. An 8-hour data

collection and monitoring period is sufficient, as QT_c intervals return to baseline within 2-6 hours.^{9,10}

At the end of this visit, and after a minimum 14-day washout period, subjects will take another of the study drugs as follows:

Group A: (n= 20 subjects)

Each subject will take oral progesterone 400 mg orally once daily (two x 200 mg capsules) in the evening for 7 days.

Group B: (n= 20 subjects)

Each subject will take two placebo capsules once daily in the evening for 7 days.

Subjects will be sent home with one week's supply of the study medication to which they are randomized for this phase and a medication diary with which to keep track of when they take the medication, any adverse effects they may experience, and any changes in their own concurrent medications. They will receive written and verbal instructions about the study medication and dates will be established for Visit 3.

At 3-7 days following the study visit, subjects will be called/texted or emailed based on preference to assess for any potential adverse events related to study medications or procedures.

Visit 3:

Prior to the visit subjects will be NPO and remain NPO until 4 hours after the end of the ibutilide dosing. Subjects may drink non-caloric drinks during this period such as coffee, tea, diet soda, water etc. If the serum potassium concentration is low as defined previously in the protocol, then the subject may have orange juice or a banana as previously defined in the protocol.^{26,27,28}

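### The crossover analysis has no period term, and sequence is not balanced within each separately analysed population of 20

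*Combined protocol and SAP*

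**What the plan says.** Section 4.0 sets the sample: "Forty volunteer subjects (n=20 postmenopausal women, n=20 premenopausal women) will be recruited". Section 5.0 gives the randomisation method as "A random number generator will be used to determine the order of randomization" and, under Visit 1, says that "subjects will be randomly assigned to two groups". These are listed as "Group A: (n= 20 subjects" and "Group B: (n= 20 subjects", with Group A on placebo first and Group B on progesterone first; Visit 2 reverses the treatments. Neither section mentions blocks or stratification by menopausal population.

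Section 8.0 states: "Statistical analysis will be performed separately for the two subject populations". The only between-phase comparison is "Paired t-test (if normality holds) or signed-rank test (if normality does not hold) will be used to compare outcome measures", with 95% confidence intervals and the choice of test made by a Kolmogorov-Smirnov test. The sample size of 20 per population "will be sufficient to detect a difference in maximum QT_F and QT_{Fra} of 15 ms". No period or sequence term appears anywhere. The 14-day minimum washout deals with carryover, not with a difference between periods.

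**The concern.** In a two-period crossover, any systematic difference between the first and second ibutilide visits adds to the progesterone-minus-placebo difference in one sequence and subtracts from it in the other. A paired test on the pooled differences cancels this only when the sequences are equal in size. Even then it leaves the period effect in the variance. Here the stated 20/20 balance applies to the wrong unit: each analysis uses 20 women of one population, and their split is neither stated nor excluded.

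The two ibutilide visits are at least three weeks apart (14 days of washout plus 7 days of dosing), so a drift of a few milliseconds is possible. At stake are the reported treatment difference and its interval in each population. The signed-rank alternative has the same gap.

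**Working it through.** **The plan's own figure.** With a 15 ms difference, SD 12 ms, two-sided α 0.05 and power 0.80, the unpaired normal formula gives 2 × (1.960 + 0.842)² × 12²/15² = 10.05 per group. Power with 10 per group is 0.798. The stated 20 thus matches a total of 20 for two independent groups. The planned paired t-test needs 8 women if the SD of within-woman differences is 12 ms, and 13 if it is 17 ms. Power is therefore not the weak point.

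**Inputs.**
- From Section 8.0: n = 20 per population, target 15 ms, SD 12 ms (attached to the ibutilide response).
- Assumed, because not given: SD of within-woman differences S = 12 ms (correlation 0.5) or 12√2 = 16.97 ms (correlation 0); period effect π (period 2 minus period 1) = 5 or 10 ms.

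**Shift.** Let τ be the effect of progesterone minus placebo. A Group A woman's difference has mean τ + π; a Group B woman's has mean τ − π. The paired mean therefore estimates τ + π(nA − nB)/n.

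| Split | Shift, π = 5 | Shift, π = 10 |
|---|---|---|
| 10:10 | 0 | 0 |
| 12:8 | 1.0 ms | 2.0 ms |
| 13:7 | 1.5 ms | 3.0 ms |
| 14:6 | 2.0 ms | 4.0 ms |

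**Chance of each split within a population of 20.**

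| | 20/20 fixed overall (hypergeometric) | Simple randomisation (binomial) |
|---|---|---|
| Exactly 10:10 | 24.8% | 17.6% |
| 12:8 or worse | 34.3% | 50.3% |
| 13:7 or worse | 11.3% | 26.3% |
| 14:6 or worse | 2.6% | 11.5% |

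**Interval width at 10:10.** The expected variance of the paired differences is S² + 4π²·nA·nB/[n(n − 1)]. For S = 12 and π = 5 this is 144 + 25 × 400/380 = 170.3, so the half-width is 2.093 × √(170.3/20) = 6.11 ms. The period-adjusted estimate averages the two sequence means; its standard error is ½S√(1/nA + 1/nB) on 18 df, so its half-width is 2.101 × ½ × 12 × √0.2 = 5.64 ms.

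| S | π | Paired half-width | Adjusted half-width | Paired wider by |
|---|---|---|---|---|
| 12 | 5 | 6.11 | 5.64 | 8% |
| 12 | 10 | 7.39 | 5.64 | 31% |
| 16.97 | 5 | 8.30 | 7.97 | 4% |
| 16.97 | 10 | 9.28 | 7.97 | 16% (17% by simulation) |

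**Coverage at 13:7 (simulation).** The paired interval covers in about 93.9% / 92.5% of trials (S = 12, π = 5 / 10) or 94.4% / 93.1% (S = 17). The adjusted interval has no shift and covers in 95%. At 14:6 with π = 10 and S = 12, paired coverage falls to about 85%.

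**Averaged over a 20/20 allocation, S = 12.** Mean bias is 0. Non-coverage is 4.2% / 2.9%, which is conservative. Mean full interval width is 12.0 / 14.5 ms, against 11.1 ms with stratified sequence and a period term.

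**Power for 15 ms at 10:10 (simulation).** 0.999 / 0.996 at S = 12, and 0.95 / 0.92 at S = 17 against 0.96 adjusted.

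**The case against.** The harm rests on a period effect that no document gives. Values of 5 and 10 ms are one third and two thirds of the whole target. At 2 or 3 ms and 10:10, the paired interval is only 1.1% or 2.9% wider (S = 12), and at 13:7 its coverage stays near 94.5% or above.

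In an unbalanced population a period term can also cost more than it saves. By mean squared error the two analyses break even at π = S/√[n(1 − r²)], with r = (nA − nB)/n. At 13:7 that is 12/√18.2 = 2.8 ms, or 4.0 ms with S = 17.

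The 13:7 case is a tail event if the stated 20/20 is enforced: 66% of populations fall at 11:9 or better, and the mean absolute shift is 0.12π. The design limits drift through fasting, triplicate ECGs, blinded reading and, for premenopausal women, matched cycle phase. The percentage-change endpoint is measured against a same-visit baseline, so drift in QTc level largely cancels there. Over randomisation the paired t-test is unbiased and its type I error is not inflated.

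All of this stands, and it limits the weight of the point. It does not remove it. One split is realised per population, and that estimate is the one reported. Baseline QTc, maximum QTc and the area endpoints have no same-visit correction. The break-even argument is a reason to balance the sequences, not to omit the period term.

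**Conclusion.** The concern holds as a recommended change, not a fatal flaw. The plan has no period term and does not secure sequence balance within the populations it analyses. If a period effect of 5 to 10 ms exists, an uneven population's estimate can plausibly move by 1.5 to 3 ms, and a balanced population's interval is 4% to 31% wider than necessary. These sizes depend on the assumed period effect and on an SD of differences of 12 to 17 ms, neither of which the documents give. With a period effect of 2 to 3 ms the consequences are small. The damage is to the estimate and interval. The stated 80% power is generally met, except in an unfavourable corner: at 13:7 with a 10 ms period effect opposing the treatment effect and S = 17, power is about 0.77 against 0.94 adjusted.

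**What to change.** 1. Randomise sequence in permuted blocks stratified by menopausal population, 10 women to each sequence in each population, and say so in Sections 4.0 and 5.0.
2. In Section 8.0, make the primary analysis in each population a crossover model with fixed treatment, period and sequence and random subject. Report the treatment difference with its 95% interval.
3. Drop the Kolmogorov-Smirnov choice of test, which lets the data select the analysis. Keep a rank-based sensitivity analysis: a rank-sum test comparing within-woman period differences between the two sequences, which also allows for period.

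The model can include women with one evaluable phase, but the gain is small and rests on a missing-at-random assumption. With assumed correlations of 0.7 to 0.3, the standard error falls by 0.3–0.8% with one such woman in 20 and by 1.5–3.6% with four. The earlier crossover's 31 doses, less 2 × 15, imply one.

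The cost is a randomisation list, some wording and one degree of freedom; SAS 9.4, already named, has the procedures. If there is no period effect, the interval is about 0.3% wider at 10:10, 2.4% at 12:8 and 5% at 13:7, so items 1 and 2 belong together. If randomisation has already begun, the period term can still be used, because each woman's sequence is known.
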